***Once a subject is taken off study, no further data can be collected.***

### 3.5.3 Off Protocol Therapy and Off Study Procedure

Authorized staff must notify Central Registration Office (CRO) when a subject is taken off protocol therapy and when a subject is taken off-study. A Participant Status Update Form from the web site (<http://home.ccr.cancer.gov/intra/eligibility/welcome.htm>) main page must be completed and sent via encrypted email to: NCI Central Registration Office [[contact]](mailto:[contact]).

## 4 CONCOMITANT MEDICATIONS/MEASURES

- Study subjects will be allowed to take multivitamins, analgesics (NSAIDS or acetaminophen), antipyretics, and antihistamines for symptomatic relief of local or systemic injection site reactions.
- Patients are allowed to continue on medications as clinically indicated for treatment of chronic medical conditions e.g. hypertension, diabetes, hypercholesterolemia, etc.
  - *Excluded* Therapy:
    - *Chemotherapy*: Concomitant use of chemotherapy is not allowed during this trial.
    - *Anti-Cancer Radionuclides*: Concomitant use of anti-cancer radionuclides is not allowed during this trial. Patients will be allowed to co-enroll in studies of novel radionuclide imaging agents e.g. F-18 NaF PET/CT for quantification of metastatic burden in prostate cancer.
    - *Hormonal Therapies*: Concomitant use of anti-androgen hormonal agents is not allowed.
    - *Alternative Medications or Nutriceuticals Known to Alter PSA*: Concomitant use of agents known to alter PSA e.g. phytoestrogens and saw palmetto is not allowed. Note: Patients receiving medications for urinary symptoms such as Flomax or 5-alpha reductase inhibitors (finasteride and dutasteride) on a chronic stable dose for at least 3 months prior to study enrollment are *allowed*.
    - *Corticosteroids*: Concomitant, *chronic systemic corticosteroids are not allowed* during this trial (excepting emergent use for clinical indications). However, the use of inhaled corticosteroids, intranasal sprays and topical creams on limited body areas *is allowed*.

### ***Vitamin D3 (Cholecalciferol) Supplementation***

Vitamin D when ingested is metabolized in the liver to 25-OH vitamin D. Inside cells, it is metabolized further by 1-hydroxylase where it is transformed into a seco-steroid hormone that is important to a host of critical cellular and immune functions within the body. Within cells is a second enzyme 24-hydroxylase whose function is to decrease vitamin D, thereby maintaining intracellular vitamin D homeostasis. The classic function of vitamin D is to regulate calcium

homeostasis and in turn, bone formation and resorption. However, additional functions of vitamin D have been demonstrated and include effects on immune response by promoting cellular apoptosis and differentiation. The exact role of vitamin D deficiency in prostate, breast, colon and other cancers has been controversial, with some laboratory studies suggesting there is a role and other epidemiological studies suggesting that there is no role or even possibly that supplementation should be avoided. In a recent study by Marshall and colleagues (43) vitamin D supplementation of 4,000 IU per day for one year was examined in men with low risk prostate cancer (Gleason score of 6, 1-6 cores positive out of 12 possible and a PSA <10) under active surveillance. After one year upon re-biopsy, 60% showed a decrease in the number of positive cores, Gleason score or both and in 6% these factors remained unchanged. In addition PSA levels did not rise. In another study reported by Wagner and colleagues at AACR in April 2012 (44), 66 men scheduled to undergo radical prostatectomy were randomly assigned to receive a daily vitamin D dose of 400, 10,000 or 40,000 IU daily for 3 to 8 weeks prior to surgery. Calcitriol levels in the prostate increased progressively with increasing vitamin D dosing and corresponded with lower levels of Ki67 as well as higher levels of specific growth-inhibitor microRNAs.

Several studies have shown that women with low vitamin D levels have an increased risk of breast cancer incidence and mortality, but research is lacking investigating vitamin D levels and prognostic variables e.g. hormone receptor status, Oncotype DX etc. in this patient population. In a case control study of 194 women s/p breast cancer surgery and 194 cancer-free controls conducted by Peppone and colleagues at the University of Rochester (45), women with breast cancer were found to have significantly lower 25-OH vitamin levels than controls (32.7ng/mL vs. 37.4 ng/mL respectively, P=0.02). Importantly, women with suboptimal 25-OH vitamin D levels (<32 ng/mL) had significantly increased odds of having ER-negative (OR = 2.59, 95% confidence interval [95% CI] = 1.08-6.23) and triple-negative cancer (OR = 3.15, 95% CI = 1.05-9.49) than those with optimal 25-OH D concentrations. In addition, women with basal-like phenotype had lower 25-OH vitamin D levels than women luminal A phenotype (24.2 ng/mL vs. 32.8 ng/mL, respectively P = 0.04). In summary, women with a more aggressive breast cancer molecular phenotype (basal-like) and worse prognostic indicators (ER- and triple-negative) had lower mean 25-OH vitamin D levels.

Given its critical role in immune function and possible role in cancer pathophysiology, all patients will have serum 25-OH vitamin D levels obtained at baseline. Although there is debate about the target level of 25-OH vitamin D for optimum health, many vitamin D experts agree that it should be greater than the 20 ng/mL recommended by the Institute of Medicine (IOM) and U.S. Food and Nutrition Board (46) and that levels of at least 40 ng/mL are necessary for optimum skeletal health as well as the other potential non-skeletal benefits of vitamin D (47).

- All patients with 25-OH vitamin D levels < 40 ng/mL will be initiated on oral supplements of Vitamin D3 (cholecalciferol) per standard clinical care guideline.

## 5 BIOSPECIMEN COLLECTION

### 5.1 CORRELATIVE STUDIES FOR RESEARCH/PHARMACOKINETIC STUDIES

This study does not involve any investigation of pharmacokinetic or pharmacodynamic parameters.

Exploratory analyses will be performed to identify vaccine characteristics using microarrays and TARP-specific cellular or humoral responses. Specific gene expression profiling of autologous ME DC vaccine products will examine genes involved in antigen uptake, apoptosis, cytokine and chemokine expression. We will also examine circulating tumor cells (CTCs) and immune subsets in peripheral blood mononuclear cells including iNKT and myeloid derived suppressor cells (MDSCs) with [name]. This will help to determine if the autologous ME TARP DC vaccination is associated with a reduction in CTCs as compared to placebo and to assess the impact of vaccination on quantitative and qualitative parameters of iNKT cells. CTCs will also be analyzed in parallel using technology from RareCyte, Inc. to compare the quantitative parameters with those obtained using the standard techniques in the [name] lab as part as the CRADA #03048 (see section [11.1.2](#)). In addition, the under the CRADA, molecular characterization of individual CTCs pre and post vaccination will also be performed.

Preliminary assessment of immune status of subjects enrolled in the first generation 09-C-0139 TARP peptide vaccine study demonstrated normal absolute lymphocyte counts, CD4 and CD8 T-cell subset absolute counts, percentages and ratios as well as excellent immunity to CEF peptide pooled antigens (CMV, EBV and Flu matrix peptide) utilized as positive controls in IFN- $\gamma$  ELISPOT assays investigating TARP-specific reactivity. We will plan to prospectively expand our characterization of immune status and senescence in subjects by exploring investigation of T-cell receptor v-beta repertoire analysis, CD4+CD25+FoxP3+ T-regulatory cell subsets and potentially T-cell receptor excision circles (TREC) as potential correlates of changes in slope log PSA/PSADT and clinical outcomes.

## **5.2 SAMPLE STORAGE, TRACKING AND DISPOSITION**

### **5.2.1 Collection and Storage of Research Samples**

For research samples obtained for investigation, the Clinical Support Laboratory, Leidos Biomedical Research processes and cryopreserves samples in support of IRB-approved, NCI clinical trials. The laboratory is located in a controlled-access building and laboratory doors are kept locked at all times. Upon specimen receipt each sample is assigned a unique, sequential laboratory accession I.D. number. All products generated by the laboratory that will be stored either in the laboratory freezers or at a central repository facility are identified by this accession I.D. An electronic database is used to store information related to patient samples processed by the laboratory. Vial labels do not contain any personal identifier information. Samples are stored inventoried in locked laboratory freezers and are routinely transferred to the NCI-Frederick repository facilities for long-term storage. These facilities are operated under a subcontract to Leidos Biomedical Research. Access to stored clinical samples is restricted. Investigators establish sample collections under “Source Codes” and the investigator responsible for the collections, typically the protocol Principal Investigator and/or Lead Associate Investigator, specifies who has access to the collection.

When requests are submitted by the NCI investigator for shipment of samples outside of the NIH it is the policy of the laboratory to request documentation that a Material Transfer Agreement (MTA) is in place that covers the specimen transfer. The laboratory does not provide patient identifier information as part of the transfer process but may, at the discretion of the NCI investigator, group samples from individual patients when that is critical to the testing process. Samples will not be sent outside NIH without IRB notification and an executed MTA.

Once primary research objectives for the protocol are achieved, intramural researchers can request access to remaining samples provided they have an IRB-approved protocol and patient consent. Access to these samples will only be granted following IRB approval of an additional protocol, granting the rights to use the material.

#### 5.2.2 Future Use / Protocol Completion / Sample Destruction

Blood, urine and tissue specimens collected in the course of this research project may be banked and used in the future to investigate new scientific questions related to this study. However, this research may only be done if the risks of the new questions were covered in the consent document. If new risks are associated with the research (e.g., analysis of germ line genetic mutations.) the Principal Investigator must amend the protocol and obtain informed consent from all research subjects.

Following completion of this study, samples will remain in storage as detailed above unless a patient has opted out of the future use of specimens and data. Currently, there is no plan to use these samples outside of the use described in the protocol.

If the patient withdraws consent, the participant's data will be excluded from future distributions, but data that have already been distributed for approved research use will not be able to be retrieved.

The PI will record any loss or unanticipated destruction of samples as a deviation. Reporting will be per the requirements of section [7.2.1](#).

### 5.3 SAMPLES FOR GENETIC/GENOMIC ANALYSIS

No genetic/genomic analyses will be performed as part of this clinical investigation.

## 6 DATA COLLECTION AND EVALUATION

### 6.1 DATA COLLECTION

1. Each patient must meet all eligibility requirements and a completed registration must be sent to the NCI Central Registration Office (CRO).
2. The Consent Document must be signed prior to registration with the CRO.
3. Treatment will be given according to protocol (on-study and treatment notes, reports of adverse events and documentation of any deviation from the study protocol).
4. Data will be entered into a secure software system (C3D Database) produced by OracleTM Corporation (Redwood Shores, CA). Data will be collected based on protocol-specific requirements, verified for accuracy and completeness. Any hard copy data will be kept in locked secure area in the Vaccine Branch Clinical Trials Offices.
5. Toxicity will be assessed according to the protocol using the CTCAE v4.0 that is available at: [http://ctep.cancer.gov/protocolDevelopment/electronic\\_applications/ctc.htm](http://ctep.cancer.gov/protocolDevelopment/electronic_applications/ctc.htm)
6. Response to autologous ME TARP DC or elutriated monocyte placebo vaccination will be assessed by calculation of slope log (PSA)/PSADT at every protocol study time point and specifically used to examine:
  - o The slope log (PSA for Weeks 3-24 minus that formed for the 12 months prior to enrollment on study (referred to as slope 324 – pre-slope) as well as the slope log (PSA) for weeks 3-48 versus the same pre-treatment slope log (PSA) (referred to

as slope 348 – preslope) in patients naïve to TARP vaccination receiving active, multi-epitope TARP vaccination *vs.* placebo.

7. Results of re-staging scans at Weeks 48 and 96 will be documented and verified that the patient remains Stage D0 without evidence of progressive disease unless the scans or clinical findings demonstrate otherwise.
8. Drug accountability records will be maintained for each patient.
9. Vaccine report cards (VRCs) associated with each autologous ME TARP DC or elutriated monocyte placebo vaccination will be obtained for each patient (see [Appendix D](#)). If the VRC is not available, investigators may describe the grade and duration of the injection site reaction based on the patient's verbal report. The information recorded on the VRC will also be documented in the medical record.
10. Personal identifiers will not be used when collecting and storing data.
11. An enrollment log will be maintained in the regulatory binder/file that is the only location of personal identifiers with unique subject identification number.

The PI will be responsible for overseeing entry of data into an in-house password protected electronic system (C3D) and ensuring data accuracy, consistency and timeliness. The principal investigator, associate investigators/research nurses and/or a contracted data manager will assist with the data management efforts. All data obtained during the conduct of the protocol will be kept in secure network drives or in approved alternative sites that comply with NIH security standards. Primary and final analyzed data will have identifiers so that research data can be attributed to an individual human subject participant.

All adverse events, including clinically significant abnormal findings on laboratory evaluations, regardless of severity, will be followed until return to baseline or stabilization of event. Serious adverse events that occur more than 6 weeks after the last administration of investigational agent/intervention and have an attribution of at least possibly related to the agent/intervention should be recorded and reported as per sections [Error! Reference source not found.](#) and [7.4](#).

AEs will be documented starting with the first study intervention through 60 days following the last administration of vaccine. Adverse events that are serious need to be recorded after 60 days following the last intervention, only if they are serious and related to the study intervention.

An abnormal laboratory value will be considered an AE if the laboratory abnormality is characterized by any of the following:

- Results in discontinuation from the study
- Is associated with clinical signs or symptoms
- Requires treatment or any other therapeutic intervention
- Is associated with death or another serious adverse event, including hospitalization.
- Is judged by the Investigator to be of significant clinical impact
- If any abnormal laboratory result is considered clinically significant, the investigator will provide details about the action taken with respect to the test drug and about the patient's outcome.

**End of study procedures:** Data will be stored according to HHS, FDA regulations and NIH Intramural Records Retention Schedule as applicable.

**Loss or destruction of data:** Should we become aware that a major breach in our plan to protect subject confidentiality and trial data has occurred, this will be reported expeditiously per requirements in section [7.2.1](#).

## **6.2 RESPONSE CRITERIA**

Since Stage D0 prostate cancer patients have biochemical PSA recurrence, with no evidence of bony or visceral metastatic disease traditional RECIST or Immune-Related Response Criteria (irRC) will not be utilized in this study.

### **6.2.1 Progression-Free Survival**

An exploratory assessment of progression free survival (PFS) will be conducted in patients receiving autologous ME TARP DC vs. autologous elutriated monocyte placebo vaccine. PFS is defined as the duration of time from start of vaccine treatment to time of progression or death.

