#### 1.1.2 Secondary Objectives:

- To assess the safety of multi-epitope TARP peptide autologous DC vaccination.
- To characterize cellular and humoral immune responses associated with multi-epitope TARP peptide autologous DC vaccination as measured by anti-TARP antibodies and TARP-specific CSFE (carboxyfluorescein diacetate succinimidyl ester) proliferation, ELISPOT (IFN- $\gamma$ , perforin and Granzyme B), intracellular cytokine staining (ICS) and tetramer assays.
- To conduct an exploratory comparative analysis of slope 324 – pre-slope and slope 348 – pre-slope differences in HLA-A\*0201 patients versus *non*-HLA\*0201 patients.
- To conduct an exploratory assessment of progression free survival (PFS) at 96 weeks in patients receiving multi-epitope TARP peptide autologous DC vaccination

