#### 3.5.2 Off-Study Criteria

- 3.5.2.1 Completion of study.
- 3.5.2.2 Removal from protocol vaccine therapy as outlined in Section [3.5.1](#).
- 3.5.2.3 Patient develops evidence of visceral or bony metastatic disease.
- 3.5.2.4 Patients with a calculated PSADT of < 3 months after a minimum of 15 weeks on study or 4 doses of vaccine. Prior to removal from study, PSA check and PSADT calculation should be repeated at the next visit in 3 to 6 weeks from the date PSADT < 3 months is identified for an off-study decision.
- 3.5.2.5 Patients with a calculated PSADT that has decreased by > 50% from their calculated Pre-NIH PSADT on or after 24 weeks on study. Prior to removal from study, PSA check and PSADT calculation should be repeated at the next visit in 3 to 6 weeks from the date PSADT decreased by > 50% is identified for an off-study decision.
- 3.5.2.6 Development of a second malignancy other than basal cell or squamous cell carcinoma of the skin that is amendable to local treatment.

- 3.5.2.7 Patient elects to withdraw from study participation at any time.
- 3.5.2.8 Patient is removed from study by the Principal Investigator or Lead Associate Investigator for reasons other than toxicity e.g. failure to adhere to study visits or due to the presence of an intercurrent medical condition, etc.
- 3.5.2.9 Investigator decision to end the study
- 3.5.2.10 Death

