1. As indicated in section **12.2**, all subjects  $\geq$  age 18 will be offered the opportunity to complete an NIH Advance Directives form. This should be done preferably at baseline but can be done at any time during the study as long as the capacity to do so is retained. The completion of the form is strongly recommended but is not required.
2. TTV Screening (Anti-HIV-1/2 Ab, anti-HCV Ab, HBsAg, HBs Ab, anti-HTLV-1/2 Ab, West Nile, T. Cruzi and RPR) must be drawn at the time of screening but for the consent, only HIV, HBV and HCV results are required to enroll. If the day of apheresis is  $>30$  days from the initial TTV screening, TTV screening needs to be repeated to be compliant with DTM requirements.
3. Historic records are acceptable if previous NIH results are available.
4. PSADT will be calculated only when the patient is in D0 prostate cancer.
5. Apheresis should occur within 3 weeks after consenting. The first dose of investigational drug should be scheduled within 6 weeks after the consent is signed. Apheresis may be repeated if additional plasma or cell aliquots are required to manufacture the vaccine.
6. Screening studies including scans should occur within 60 days of enrollment at the NIH unless otherwise specified (see section **2.2.2**).
7. Evaluation to proceed with vaccine administration should occur within 10 days prior to administration. Study weeks will be numbered so that they match vaccine dose weeks, in case off-target dates in investigational product administration occur. The dosing interval should be at least 14 days.
8. Evaluations at Week 3 serve as baseline. If amylase, lipase, lipid panel, TSH, 25-OH Vitamin D, lymphocyte phenotyping, urinalysis have already been completed within 30 days prior to the first dose of administration of investigational product, they do not need to be repeated at the baseline (Week 3) timepoint. Historic HLA-ABC, DR results from NIH may be used for baseline.
9. Post-therapy follow up, with the patient or patient's local oncologist, will occur annually until disease progression or death.
10. Research correlatives on week 12 (post 3 doses of investigational treatment) may be collected 7 days (+/- 3 days) post 3rd dose of investigational treatment, if patient is available locally.

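### The bar on data after a man leaves the study contradicts the planned follow-up to progression or death; taken as written, it ends PFS observation in men removed under the PSADT rules

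*Combined protocol and SAP*

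**What the plan says.** - **PFS.** Section 6.2.1 plans an exploratory comparison of the arms: "PFS is defined as the duration of time from start of vaccine treatment to time of progression or death". Section 1.1.2 sets the horizon, but for vaccine recipients only: "To conduct an exploratory assessment of progression free survival (PFS) at 96 weeks in patients receiving multi-epitope TARP peptide autologous DC vaccination". Neither 6.2.1 nor Section 10 defines progression, gives a censoring rule or names an analysis method for PFS.
- **Scans.** Restaging is scheduled at Weeks 48 and 96 (Sections 3.2 and 6.1). Section 6.1 also allows clinical findings to show progression.
- **PSADT removal.** Criterion 3.5.2.4 covers "Patients with a calculated PSADT of < 3 months after a minimum of 15 weeks on study or 4 doses of vaccine". Criterion 3.5.2.5 covers "Patients with a calculated PSADT that has decreased by > 50% from their calculated Pre-NIH PSADT on or after 24 weeks on study". For both: "Prior to removal from study, PSA check and PSADT calculation should be repeated at the next visit in 3 to 6 weeks". Both take the man off study, not only off vaccine.
- **After removal.** The statement that closes Section 3.5.2, just before 3.5.3, reads "Once a subject is taken off study, no further data can be collected".
- **Follow-up.** Appendix A footnote 9 says post-therapy contact with the patient or the local oncologist "will occur annually until disease progression or death". Nothing says which statement prevails.
- **Completers.** Section 3.5.1.3 lists finishing the six doses and the safety visit as removal from therapy, and 3.5.2.2 makes removal from therapy an off-study criterion.

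**The concern.** A man removed for a short or halved PSADT has, by definition, no metastasis recorded so far and a PSA rising faster than the rules tolerate. If data collection stops there, a later metastasis or death cannot enter PFS and he can only be censored. Standard time-to-event estimates assume that a censored man has the same outlook as those still under observation. That assumption fails if PSA slope predicts metastasis. If the vaccine also slows PSA, as the sample-size section assumes, placebo men are removed more often, so placebo PFS is overstated more than vaccine PFS. PFS is exploratory, but it is the plan's only clinical efficacy outcome, and Section 12.4 presents it as the look at clinical benefit. Status that was not collected cannot be recovered at analysis.

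**Working it through.** **1. The plan's own figure.** Section 10 gives a slope-change difference of 0.048, SD 0.072, 44 vs 22 men and one-sided 0.05. The standardised difference is 0.048/0.072 = 0.667. The noncentrality is 0.667/√(1/44 + 1/22) = 2.55, and the noncentral t with 64 df gives 81.1% power (stated: 81%). The slope inputs therefore reproduce. The plan states no event count, hazard ratio or power for PFS.

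**2. Timing.** Appendix G first calculates on-study PSADT at Week 15. With 3-6 weeks for confirmation, the earliest removal is Week 18-21 under 3.5.2.4 and Week 27-30 under 3.5.2.5. Both precede the Week 48 scan.

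**3. Chance of meeting a PSADT rule.** Take slope = ln 2/PSADT per month (assumed units; the pilot's 0.0042/day is 0.128/month, a PSADT of 5.4 months). Let s be the baseline slope. The first rule is met when the slope change exceeds ln 2/3 − s, the second when it exceeds s. With c the smaller of the two, P = 1 − Φ((c − μ)/0.072), where μ = −0.033 (active) or +0.015 (placebo).

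Example at PSADT 15 months: s = c = 0.0462. Active: (0.0462 + 0.033)/0.072 = 1.10, so 14%. Placebo: (0.0462 − 0.015)/0.072 = 0.43, so 33%.

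| Baseline PSADT (months) | Active | Placebo |
|---|---|---|
| 15 | 14% | 33% |
| 9 | 6% | 20% |
| 6 | 2% | 8% |
| 4 | 10% | 28% |
| Uniform 3-15 (assumed) | 8.5% | 23.1% |

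That is about 0.085 × 44 = 4 active and 0.231 × 22 = 5 placebo men.

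**4. Effect on 96-week PFS.** This is a simulation of 1,000,000 men per arm. Assumptions not in the documents: progression means metastasis, placebo progression is about 30% by Week 96, hazard is multiplied by exp(b) per 0.072 of on-study slope, and all removals come before Week 48. Some rows add a direct hazard ratio (HR) of 0.7 for the vaccine. Entries are PFS % active/placebo, with the difference in points from unrounded values.

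| b | Direct HR | Removed men followed | Removed men censored | Shrinkage |
|---|---|---|---|---|
| 0.5 | 1.0 | 77.1/70.0 (7.1) | 79.1/75.0 (4.1) | 42% |
| 1.0 | 1.0 | 81.1/70.1 (11.0) | 84.4/78.7 (5.7) | 48% |
| 0.5 | 0.7 | 83.0/69.9 (13.1) | 84.6/74.9 (9.8) | 25% |
| 1.0 | 0.7 | 85.6/70.0 (15.6) | 88.5/78.6 (9.9) | 37% |

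In these rows 36-45% of placebo and 17-27% of active progressions fall in removed men. Counting removal as progression gives differences of 14.7, 16.8, 19.8 and 20.5 points, so the unwritten rule matters as much as the bias.

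Two boundary cases:
- With b = 0, followed and censored differences are equal (7.9 points each with direct HR 0.7).
- With no vaccine effect, the difference is zero either way. For b = 0.5, though, both arms' PFS is overstated (70.0% becomes 75.0%).

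**5. Sensitivity.** A visit-by-visit simulation assumed true slope-change SD 0.055, residual log-PSA SD 0.13 and hazard 1.6-2.7 times higher per +0.1/month. It gave removal of 11% active and 29% placebo, and shrinkage of 42-52%. A rerun of those assumptions with PSADT fitted to all on-study values gave 7%, 24% and 31-44%. Appendix G asks for PSADT over both the whole study and the prior 6 months; 3.5.2 does not say which one triggers removal.

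**6. Precision.** With 19% vs 30% progression (assumed), the SE of the difference is √(0.19 × 0.81/44 + 0.30 × 0.70/22) = 0.114, about 11 points.

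**The case against.** **The off-study text cannot be meant literally.** Read literally, 3.5.1.3 with 3.5.2.2 takes every completer off study 3-6 weeks after the Week 24 dose. That would abolish the Week 36-96 visits, both scans and the Week 3-48 primary endpoint. Read less literally, footnote 9 can operate and much of the loss may disappear. This stands. It makes the contradiction wider and the loss less certain.

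**The plan states no biased analysis.** It names no estimator or censoring rule for PFS and leaves progression undefined. The metastatic reading is an inference. It is supported by the pilot's off-study table, which lists progression (12 men) apart from PSADT criteria (2 men), and by 3.5.2.3, but it remains an assumption.

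**The size rests on assumptions.** The pilot lost 2 of 41 men to PSADT criteria. All were vaccinated, so this bears only on the active rate; at a true 9-11%, seeing 2 or fewer of 41 has probability 27-16%. The pilot's rule is not given, and one man left at Week 9, so it may have differed. The shift of about 3 to 6 points in step 4 is at most about half an SE.

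**Later treatment may undo the gain.** Section 4 bars hormonal therapy and chemotherapy during the trial, but men who have left are not bound by it. If later therapy multiplies hazard by 0.3-0.5 (assumed), the visit-level rerun gives 1.1-7.8 points with follow-up against 1.6-6.2 with censoring. At the weaker slope link, follow-up can give the smaller difference (1.8 vs 2.6). This stands and belongs among the fix's downsides.

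**Conclusion.** The contradiction between the closing statement of 3.5.2 and footnote 9 is in the text and must be reconciled. If the closing statement governs, PFS observation ends early in men selected on PSA behaviour: about 9% of active and 23% of placebo men on the plan's slope figures and a uniform baseline PSADT.

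The effect on the 96-week difference is conditional. It needs a vaccine effect on PSA, a link from slope to metastasis, and progression read as metastatic disease. Under those conditions the shrinkage is roughly a quarter to a half. The simulation in step 4 leans high, because it places every removal before Week 48.

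A reader might infer that these metastases will certainly go unrecorded, that the rules remove the fastest-rising men, and that a real PFS benefit will be hidden. The documents do not support that. Footnote 9 may supply the events. The halving rule is relative to each man's own baseline. Section 12.4 calls the link from PSA slowing to clinical outcome unproven. An exploratory comparison of 44 with 22 men is imprecise in any case. The point merits correction as a matter of data capture and pre-specification; it does not touch the primary slope analysis.

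**What to change.** 1. Reconcile 3.5.1.3, 3.5.2.2 and the closing statement of 3.5.2 with footnote 9 and the Week 36-96 calendar. State that progression and survival status is still recorded to Week 96 for men who leave under 3.5.2.4 or 3.5.2.5, from the annual contact and routine care, subject to consent.
2. In 6.2.1, define progression. State that PFS is not censored at a PSADT removal when later status is known.
3. Add two supporting analyses: one that censors at PSADT removal and one that counts it as an event.
4. Record the start date of any anticancer therapy begun after removal.

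The PSADT rules themselves are unchanged. The cost is protocol wording and a few contacts of a kind the calendar already lists. Downsides: progression after removal is dated less uniformly, because it comes from outside imaging, and therapy started after removal can dilute or even reverse the gain in the arm difference. That is why its start date is needed and why the censored analysis is kept alongside.
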